## **21. Handling missing data**

We will perform complete case analyses. Excluded patients will be described against the others to evaluate a possible selection bias. The methodology described in the section 16 will be applied.

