## **10. Sample size**

For the primary objective, we expect a sensitivity of 95%. We aim to include 73 patients for a maximum length of the 95% confidence interval equals 10% (+/-5%). Assuming a NSTEMI prevalence of 10%, 730 patients must be analyzed to achieve this precision. By anticipating a 10% rate of non-exploitable data (missing value, lost to follow-up, etc.), 800 inclusions are necessary.

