## **19. Proposition and validation of a predictive tool for pre-hospital rule-out and rule-in**

The cohort will be divided into two parts: two thirds for learning and one third for validation. The description of the two samples will be performed with the same baseline variables listed in the section 16. No p-value will be computed because of the random allocation of the patients. Instead, standardized mean differences will be estimated to evaluate the comparability of the two samples.

From the learning sample, a logistic model will be estimated with LASSO penalization to select the subset of predictors among the following list of candidates: age, gender, body mass index, active smoking, stented heart disease, bypassed heart disease, compatible clinical history, delay after onset of pain lower than 3h; normal ECG evaluated by the HEMS, and the following risk factors: hypertension, diabetes, hypercholesterolemia, family history and hs-cTnI. The outcome will be the diagnosis of NSTEMI. We will perform a 20-fold deviance-based cross-validation to choose the best tuning parameter.

A particular attention will be paid to the interaction between hs-cTnI and the delay after onset of chest pain because the level of troponin may continue to grow up to three hours after the chest pain. This may lead to increase the proportion of false negatives.

From the validation sample, we will estimate its discriminative capacities by the ROC curve and the related AUC. Its goodness-of-fit will be evaluated by a calibration plot of the observed probabilities against the mean predicted probabilities for five subgroups of equal size. The corresponding Hosmer and Lemeshow statistic will be estimated.

Always from the validation sample, we will compute the in-hospital HEART score at 0h, the related ROC curve and AUC, and its difference with the pre-hospital predictive model.

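### Complete-case analysis drops any patient missing one of 14 candidate predictors from building and validating the tool; predictors should be imputed, with complete cases as a sensitivity analysis

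*SAP*

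**What the plan says.** SAP section 21 is short. Its rule is "We will perform complete case analyses", and its only follow-up is "Excluded patients will be described against the others to evaluate a possible selection bias", using the descriptive methods of section 16. No imputation and no sensitivity analysis are planned. Section 22, on assumptions, addresses model specification but not missingness.

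Section 19 fits a LASSO-penalised logistic model to "select the subset of predictors among the following list of candidates". The list has 14 entries: age, gender, body mass index, active smoking, stent, bypass, compatible history, pain delay under 3 h, normal ECG, hypertension, diabetes, hypercholesterolemia, family history and hs-cTnI. The cohort is split 2:1 into learning and validation samples. Section 20 then reads results off the validation sample at predicted probabilities of 0.3 and 0.65.

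The SAP expects some missing data. Section 16 plans to report numbers of missing values for baseline variables, and section 10 says "By anticipating a 10% rate of non-exploitable data (missing value, lost to follow-up, etc.), 800 inclusions are necessary". That allowance belongs to the primary objective: "Assuming a NSTEMI prevalence of 10%, 730 patients must be analyzed to achieve this precision". The flowchart in section 12 mentions exclusions for missing diagnoses or events, not for missing predictors.

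**The concern.** A model with 14 inputs, fitted and validated on complete records only, discards a patient for one unrecorded item such as body mass index or family history, even when hs-cTnI and the diagnosis are known. Two things are at stake.

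- **Precision.** The tool has few events to begin with, and the results in section 20 rest on one third of the cohort.
- **Who the results describe.** The AUC, calibration, NPV, PPV and the shares ruled in or out would refer to patients with complete records. If completeness is related to the outcome, the predicted probabilities themselves are shifted. The cut-offs in section 20 are absolute probabilities, so a shift matters more there than for the AUC.

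Section 21 also leaves open whether complete cases are defined once for the whole study or separately for each analysis. If once, a missing covariate would also remove patients from the primary threshold analysis, which does not use covariates.

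**Working it through.** **Inputs.** From section 10: expected sensitivity 95%, half-width 5 points, prevalence 10%, 730 to be analysed, 800 included, 10% allowance. From section 19: 14 candidate predictors and a 2:1 split. The missing rate per predictor, m, is not in the SAP and is assumed below, equal for all predictors.

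**Step 1: the plan's own figures.** 1.96² × 0.95 × 0.05 / 0.05² = 72.99, so 73 events, and 73 / 0.10 = 730. Allowing 10%, 730 / 0.9 gives 812 and 730 × 1.1 gives 803; the stated 800 is close to both. The calculation reproduces, and it concerns sensitivity only.

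**Step 2: loss from requiring all 14 predictors.** With independent gaps the loss is 1 − (1 − m)^14. If gaps always fall in the same patients it is m; if they never coincide it is 14m. Complete cases are 800 × (1 − loss), with no other loss. Events are 10% of these, split 2:1, assuming completeness is unrelated to the outcome.

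| m | Loss if independent | Range m to 14m | Complete of 800 | Learning / validation events |
|---|---|---|---|---|
| 0 | 0% | – | 800 | 53.3 / 26.7 |
| 0.5% | 6.8% | 0.5–7% | 746 | 49.7 / 24.9 |
| 0.75% | 10.0% | 0.75–10.5% | 720 | 48.0 / 24.0 |
| 1% | 13.1% | 1–14% | 695 | 46.3 / 23.2 |
| 2% | 24.6% | 2–28% | 603 | 40.2 / 20.1 |
| 3% | 34.7% | 3–42% | 522 | 34.8 / 17.4 |

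The independent loss reaches 10% at m = 1 − 0.9^(1/14) = 0.75%.

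**Step 3: effect on a section 20 result.** Section 7 wants a PPV of 65% in at least 10% of patients. One third of 800 is 267, so about 27 are ruled in: 1.96 × √(0.65 × 0.35 / 27) = 18 points. At m = 2%, 603 / 3 = 201, so about 20 are ruled in and the half-width is 21 points.

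**Step 4: effect on the primary analysis if one complete-case set served everything.** At m = 2%, 60.3 events remain: 1.96 × √(0.95 × 0.05 / 60.3) = 5.5 points, against the planned 5.

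**Step 5: when bias arises.** A logistic model was simulated (assumed intercept −2.9 and slopes 1.2 and 0.5, 400,000 patients, 9.1% events) with about 25% of patients dropped. The last column is the share of events among those kept.

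| Missingness depends on | Intercept | First slope | Events |
|---|---|---|---|
| nothing dropped | −2.90 | 1.20 | 9.1% |
| nothing (random) | −2.90 | 1.20 | 9.1% |
| a predictor only | −2.90 | 1.19 | 7.0% |
| the outcome only | −3.24 | 1.20 | 6.7% |
| outcome and predictor jointly | −3.29 | 0.67 | 4.5% |

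The outcome-only shift of −0.34 moves a true probability of 0.30 (logit −0.847) to logit −1.189, a prediction of 0.23. It moves 0.65 (logit 0.619) to logit 0.277, a prediction of 0.57. In the predictor-only row the coefficients hold, but the case mix of those kept has changed.

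**The case against.** A reader might infer that complete-case analysis is certain to lose more than the 10% allowed for. The documents do not support that.

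- No missing rate is given. Passing 10% needs an average above 0.75% per predictor with roughly independent gaps. At 1–3% with fully overlapping gaps the loss is 1–3%.
- The predictors are not equally exposed. Age, ECG and time since onset bear on eligibility (sections 8 and 9), gender is basic, and hs-cTnI would not be imputed. For the other nine at 1% each, the independent loss is 1 − 0.99^9 = 8.6%, and 10% is reached at 1 − 0.9^(1/9) = 1.2%.
- The 10% is an allowance for the primary objective, which needs only hs-cTnI and the diagnosis. The tool is a secondary objective with no sample-size claim to breach. Counts of 48 learning and 24 validation events already have that 10% removed (720 × 10%, split 2:1), so they should not be used as a starting point with nothing missing.

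A reader might also infer that the tool will be biased because histories are less complete in sicker patients. The SAP says nothing of the kind, and missingness that depends only on modelled predictors leaves the coefficients intact.

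Finally, imputation can do harm. Leaving the outcome out of the learning imputation weakens the coefficients. Using it in the validation sample leaks it into the performance measures. Stacked copies of one patient can land in different cross-validation folds.

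All of this stands as a limit on the size of the claim and as a constraint on the remedy. It does not answer the remaining point: usable patients are discarded, and nothing planned corrects or tests for the consequence.

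**Conclusion.** The concern holds in a conditional form. Complete-case analysis is the only method planned for a 14-candidate model, and the description of excluded patients is a diagnostic, not a correction. The size depends on unknown missing rates: 7% to 25% of patients for 0.5% to 2% per predictor under independence, less with overlap. Starting from 53/27 events, that costs about 7/3 events at 1% (leaving 46/23) and about 13/7 at 2% (leaving 40/20), if there is no other loss and completeness is unrelated to the outcome.

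Bias cannot be asserted, only that the plan has no protection against it. Dependence on the outcome would disturb calibration and the results at both cut-offs; dependence on outcome and predictor jointly can also distort slopes. Even with sound coefficients, the shares ruled in and out describe patients with complete records. The primary analysis is affected only if a single complete-case set is used throughout, which section 21 does not settle. This should be changed, but it concerns secondary objectives.

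**What to change.** In section 21:

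- Define complete cases separately for each analysis, and state that the primary threshold analysis requires only hs-cTnI and the discharge diagnosis.
- For sections 19 and 20, multiply impute missing predictors by chained equations. Do not impute hs-cTnI or the outcome.
- Include the outcome in the imputation model for the learning sample. Impute the validation sample separately, without using its outcome.
- Fit the LASSO on the stacked imputations with weights, so that each patient counts once, and assign the 20 cross-validation folds by patient so that copies stay together.
- Pool the AUC, NPV, PPV and the shares ruled in or out over imputations.
- Keep complete cases as a sensitivity analysis, along with the planned description of excluded patients.

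Since hs-cTnI is not imputed, patients without it are still lost. If m = 2% applied to it as well, 784 of 800 would remain (784 × 10%, split 2:1: about 52/26 events), against 603 under complete cases with independent gaps.

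The cost is moderate extra programming and a more complex LASSO step. No additional data are needed.

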## **22. The assumptions of the statistical methods, and alternative methods if they are false**

The main assumption is the good specification of the predictive model. In case of a poor goodness-of-fit, we will use B-splines to evaluate the better respect of the log-linearity assumption.

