- To estimate its discriminative capacities by estimating the AUC and comparing its value with the one of the in-hospital HEART score estimated at 0h.
- To estimate its ability to rule-out the patients instead of the in-hospital evaluation at 0h for relieving emergency services, i.e., to achieve a negative predictive value equals to 99% (3) for at least 5% of the patients.
- To estimate its ability to rule-in the patients in the cardiology department instead of the in-hospital evaluation at 0h for reducing the time to treatment of the MI, i.e., to achieve a positive predictive value equals to 65.0% (Figure 1) for at least 10% of the patients.
- To evaluate its increase of capacities for discriminating patients with NSTEMI by considering additionally the venous troponin measured in hospital (difference in the AUC).

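### Minor: the tool's only described fit check is made in the validation third, where it is weak and can prompt a model change; choose the form in the learning sample and freeze it first

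*SAP*

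**What the plan says.** SAP section 19 splits the cohort two thirds to one third and fits a LASSO logistic model for NSTEMI in the larger part. The one data-driven choice placed there is the penalty: "We will perform a 20-fold deviance-based cross-validation to choose the best tuning parameter". Assessment then moves to the smaller part: "From the validation sample, we will estimate its discriminative capacities by the ROC curve and the related AUC. Its goodness-of-fit will be evaluated". The means named for this are a five-group calibration plot, with groups of equal size, and the Hosmer-Lemeshow statistic.

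Section 22 states: "The main assumption is the good specification of the predictive model". Its only remedy is conditional: "In case of a poor goodness-of-fit, we will use B-splines to evaluate the better respect of the log-linearity assumption". It does not say in which sample fit is judged, what counts as poor, which predictor would be splined, where the splines would be fitted, or whether the model is fixed before validation begins.

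The validation third also supplies the comparison with the HEART score (section 7: "comparing its value with the one of the in-hospital HEART score estimated at 0h"; section 19) and the rule-out and rule-in percentages of section 20.

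Two smaller points concern section 19. The candidate list ends "hypertension, diabetes, hypercholesterolemia, family history and hs-cTnI" and gives no scale for hs-cTnI. The section also says "A particular attention will be paid to the interaction between hs-cTnI and the delay after onset of chest pain", but no product term is among the candidates.

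**The concern.** A validation sample gives an independent assessment only if the model is settled before its results are seen. Here the sole described trigger for changing the model's form is a check that section 19 places in the validation patients. If the check fires and the model is changed, the AUC, the HEART comparison and the utility percentages no longer come from patients untouched by model building.

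The more practical worry is the reverse. The assumption that the SAP itself ranks first is guarded only by a five-group check on about 24 events. A poor form for the key predictor may pass unnoticed, and a sound model may be flagged by chance. The learning sample has twice the events and already has a planned criterion that could settle the form.

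**Working it through.** **Plan's own figures (section 10).** With 95% sensitivity and ±5% precision, n = 1.96² × 0.95 × 0.05 / 0.05² = 72.99, so 73 cases; 73 / 0.10 = 730. This agrees with "Assuming a NSTEMI prevalence of 10%, 730 patients must be analyzed to achieve this precision".

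**Size of each part (section 19 split applied to 730).**
- Learning: 730 × 2/3 ≈ 487 patients, about 49 NSTEMI.
- Validation: 730 / 3 ≈ 243 patients, about 24 NSTEMI.
- Each calibration group: 243 / 5 ≈ 49 patients, about 5 events on average. The exact 95% interval for 5/49 is 3.4% to 22.2%.

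**Can the check tell a wrong form from a right one?** The SAP gives no hs-cTnI distribution, effect size or cut for poor fit, so these are assumed: log-normal hs-cTnI with log-SD 0.8 to 1.5, three other predictors, near-unpenalised fits and Hosmer-Lemeshow on five groups (5 df). The cut is p < 0.05, which is section 13's general level and is not tied there to this statistic.

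| Setting | Wrong form flagged | Right form flagged |
|---|---|---|
| Truth linear in log, raw entered (several runs) | about 5 to 14% | 10 to 19% |
| Truth linear in raw, log entered (two runs) | 19 to 41% | 12 to 20% |
| hs-cTnI as sole predictor, log truth, log-SD 0.5 to 1.5 | 9 to 39% | 11 to 14% |

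Under log truth with other predictors the check does not separate the two forms. In the other settings it separates them only partly, and it still misses most wrong forms. The right form is flagged more often than 5% because its coefficients are themselves estimated from about 49 events.

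**What the learning sample could do.** The 20-fold cross-validated deviance picked the right scale (raw or log) in 82 to 99% of trials across runs. With LASSO over 14 candidates under log truth it did so in 89 to 98%. A closer like-for-like comparison uses a 5% likelihood-ratio test of form in the learning sample, with hs-cTnI as sole predictor. It detected the wrong form in 44 to 100% of runs, against 9 to 39% for Hosmer-Lemeshow in the validation third.

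**Optimism from a validation-triggered refit.** The simulated mean is at most 0.004 AUC. For comparison, the Hanley-McNeil variance at AUC A = 0.79 with 24 events and 219 non-events uses Q₁ = A/(2 − A) = 0.653 and Q₂ = 2A²/(1 + A) = 0.697:

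SE² = [A(1 − A) + 23(Q₁ − A²) + 218(Q₂ − A²)] / (24 × 219) = 0.0032

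This gives SE = 0.057 and a 95% half-width of about 0.11.

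**AUC lost by a wrong scale.**
- Log truth, raw entered, full-model AUC near 0.79: for example 0.788 − 0.768 = 0.020 at log-SD 0.8; about 0.055 at log-SD 1.5 (0.784 against 0.729). A second run gave 0.015 to 0.057.
- Raw truth, log entered, same AUC: 0.002 to 0.010 in one run, 0.009 to 0.018 in another.
- Log truth, raw entered, hs-cTnI sensitivity about 0.9, nearer section 10's 95%: about 0.003 to 0.011.
- Right scale entered: nil.

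**Cost of choosing the hs-cTnI form in the learning sample when the right scale would have been used anyway.** Log truth: 0.788 − 0.785 = 0.003, 0.781 − 0.778 = 0.003, 0.783 − 0.781 = 0.002, 0.784 − 0.783 = 0.001. Raw truth: 0.002, 0.003, 0.002, 0.001.

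**Interaction.** With half the patients under 3 hours, omitting the product costs 0.013 AUC if the early slope is a quarter of the later one, 0.003 at half, and nil at three quarters.

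**The case against.** Section 22 names no sample and says only that B-splines will be used to evaluate log-linearity. It does not say that the model will be refitted or re-scored. A reader might infer that the SAP plans to tune the model on its validation patients and that the reported AUC will therefore be materially inflated. The document does not support that. The link between the two sections is an inference from there being only one described fit check, and even if a refit followed, the expected optimism (0.004) is far below the sampling error (half-width 0.11). What stands is that nothing in the text prevents it.

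A reader might also take 0.02 to 0.06 AUC as the loss built into the plan. That is not supported either. It requires raw entry, which the SAP does not state, and a full-model AUC near 0.79. In one run at a full-model AUC of about 0.80, hs-cTnI alone had a sensitivity of only 0.67 at its Youden threshold, well short of the 95% in section 10. A strong marker ranks patients almost equally well on either scale.

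Three further objections stand and shape the fix. Log-linearity also concerns age and body mass index, so a rule for hs-cTnI alone would leave them unchecked. Picking one of two scales is right half the time by chance, so those percentages cannot be set directly against a test's rejection rate. Most of the simulations were not of the planned LASSO over 14 candidates.

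The interaction is already announced in section 19, and section 15 plans a subgroup under three hours. Listing the product is therefore a clarification with a small or nil gain.

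**Conclusion.** The point holds as a minor one, confined to the secondary-objective prediction tool. The primary thresholds and single-marker AUCs are untouched. As written, a weak check on about 24 events can both miss a wrong form and prompt a change to the model being validated on the same patients.

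The event counts follow from the SAP. The flagging rates and AUC losses rest on an assumed marker distribution, assumed effects and an assumed 5% cut, and should be read as ranges. The case for changing the text is that a better-placed criterion is already in the plan and costs almost nothing to use. It does not rest on a large expected gain in AUC.

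**What to change.** **Sections 19 and 22.** State that the form of every continuous candidate is chosen in the learning sample only: hs-cTnI as raw, log or a low-df spline; age and body mass index as linear or a low-df spline. The choice is the set of forms with the lowest 20-fold cross-validated deviance, using the same folds throughout. Fix the spline degree and knots in advance.

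**Section 19.** State that the model is frozen before any validation result is seen. Validation calibration is reported but does not change the validated model, and any later revision is labelled exploratory.

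**Optional.** List hs-cTnI by delay under 3 hours as one LASSO candidate. A single product matters: a cubic B-spline with two interior knots has five columns, and multiplying each by delay would turn one column into ten.

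**Cost.** SAP wording only, with no new data. It adds a few penalised terms on about 49 learning events. About 0.002 to 0.003 AUC is lost if the right hs-cTnI scale would have been used anyway. That figure was obtained for hs-cTnI alone; the added choice for age and body mass index was not simulated, which is a further reason to keep the splines small.
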